#### C.4.2 Heart Team Procedures

Each center will utilize a Heart Team to make determinations regarding eligibility of the prospective subject to be randomized in the SURTAVI trial.

##### C.4.2.1 Heart Team Composition

Local Heart Teams must be comprised of a multidisciplinary team qualified by education and experience to determine appropriate patient treatment.

##### **Minimum Membership**

- Interventional Cardiologist - ≥ 1 representative is required
- Cardiac Surgeon - ≥ 1 representative is required

##### **Additional Membership Considerations**

Additional members of the Heart Team should be included based on current standard practices and patient specific consideration, including but not limited to:

- Echocardiographer
- Anesthesiologist
- Cardiologist (general or referring physician)
- Geriatrician
- Neurologist or stroke specialist
- Radiologist or imaging specialist
- Heart Failure specialist
- Intensivist
- Nurse(s)
- Social Worker

##### C.4.2.2 Heart Team Review and Decision

Prior to determining if a patient is eligible for randomization the Heart Team will review each patient's screening data and confirm the following:

- STS risk calculation was properly performed
- Any additional risk factors not accounted for in the STS risk calculator that may increase the level of surgical risk:
  - Heart Team should consider the following potential incremental risks:
    - Age ≥ 75
    - BNP ≥ 550pg/mL or NT proBNP ≥ 3200pg/mL
    - Prior Stroke/TIA
    - FEV1 750-1000cc
    - Home / Supplemental oxygen
    - Nocturnal Bi-level Positive Airway Pressure
    - 5-Meter Gait Speed ≥ 6 seconds
    - Severe Diastolic Dysfunction (Grade III or IV)
    - Liver Disease (Child A or B)
    - Pulmonary Hypertension (systolic pressure 60-80mmHg)
    - Frailty (eg. BMI <21 kg/m^2, Albumin <3.5 g/dL, etc.)
    - Other risks, as deemed applicable
  - Confirm the incremental risk, as determined by the Heart Team, does not result in a risk definition higher than intermediate risk
- All inclusion criteria are met and none of the exclusion criteria

Both the reviewing Interventional Cardiologist and Cardiac Surgeon(s) must unanimously agree the patient has a predicted risk of operative mortality ≥ 3% and < 15% and appropriate for trial enrollment. The decision of the local Heart Team must be documented on the "Heart Team Decision" form and signed by the reviewing Interventional Cardiologist and Cardiac Surgeon(s).

---

 US only - Protocol criteria for Heart Team approval may not meet the minimum requirements outlined by Centers for Medicare and Medicaid Services (CMS) for reimbursement. Reference **Appendix R.25** for additional information.

### C.4.3 Screening Committee

The Screening Committee will ensure appropriate and consistent patient selection across all sites. Prior to the onset of the trial, a charter will be drafted to that outline roles and responsibilities as well as describe the Screening Committee process.

Final decisions on patient eligibility will be made by the Screening Committee.

### C.4.4 Roll-in Subjects

For participating centers who meet the requirement of 30 cumulative TAVI procedures but have no previous CoreValve experience (eg. Investigational centers where CoreValve is not commercially available and/or centers that did not participate in the US Pivotal Extreme/High Risk protocols) the first three successfully enrolled subjects will be considered “roll-in” subjects, will not be randomized, and will automatically be assigned to TAVI. A maximum of three successful roll-in subjects are allowed per center.

The purpose of the roll-in subjects is to provide investigators the time for training and familiarization with the investigational TAVI device. The Training and Education team will review recommendations made by Medtronic field support, Medtronic CoreValve Proctors and the Steering Committee for transition of sites from the roll-in phase to the randomization phase of enrollment after the first three subjects have been treated.

A subject will be considered a treated roll-in subject once the TAVI delivery catheter system (DCS) is introduced into the subject. A site must have three treated roll-in subjects before they can be evaluated to move into the randomization phase. The Training and Education team or designee will review and document their decisions based on the technique of the investigators, as well as the frequency, severity and nature of events in the roll-in subjects.

Roll-in subjects will complete in-clinic follow-up evaluations at the following time points post implant as subjects randomized to TAVI. However, the results for the roll-in population will be analyzed separately from the randomized population.

### C.4.5 Enrollment and Randomization

Prior to randomization and enrollment of a subject, the following must occur:

- Confirm patient signed informed consent
- Confirm patient meets all of the inclusion and none of the exclusion criteria, including approval by the Heart Team

Subjects will be considered enrolled into the trial at the time of randomization (i.e. time of treatment assignment). Randomization will occur only if the patient meets all inclusion criteria and does not meet any exclusion criteria and has been assessed by the Heart Team as being an appropriate candidate for randomization in the SURTAVI trial.

Due to the inclusion/exclusion criteria, not all patients that consent to the trial will be enrolled. All sites will be required to maintain a record of patients screened for the trial meeting general inclusion criteria who have signed the approved informed consent document. For subjects that do not meet trial criteria, the reason for not continuing in the trial must be documented and recorded in the EDC system. Patients consented but not randomized will be considered screen failures and no further trial-related follow-up will be required.

Subjects must have their TAVI or SAVR procedure no later than 30 days post-randomization.

Trial randomization will not be blinded. Once randomization is complete and a treatment arm is assigned, crossover from SAVR to TAVI treatment is not permitted. The sponsor will strictly monitor device dispensation to ensure that only those subjects randomized to the TAVI treatment arm receive the Medtronic CoreValve™ TAV.

Distribution of the subjects within the trial groups will be controlled at the implanting sites by means of central randomization using interactive voice/web randomization service (IXRS). The randomization scheme will be securely stored at the IXRS provider.

---

 Based on protocol design, the time of enrollment will be the same as randomization which is a deviation from ISO 14155 (2011).

Randomization with an assignment to the treatment arm or control arm (TAVI or SAVR) will be executed in a 1:1 ratio. Stratified randomization by investigational site and by the need for coronary revascularization will be used to ensure subjects will be allocated to each comparison group proportionately. Additionally, a blocked randomization scheme with random block sizes will be used within each stratum.

#### C.4.6 Baseline Assessments

The following baseline assessments should occur within 14 days prior to the index procedure.

- Physical examination
  - Vital signs
  - Major system findings
  - Skin assessment – refer to Radiation Exposure and Data Collection, **Appendix R.23**
- NYHA classification
- Concomitant medications
  - Use of relevant medications (diuretics, aspirin, anticoagulants, ACE-I, ARB, beta-blockers, statins and anti-platelets)
- Routine Laboratory Tests:
  - Complete Blood Count
    - White Blood Count
    - Hematocrit
    - Hemoglobin
    - Platelet Count
  - Creatinine and Creatinine Clearance
  - Cardiac Enzymes (CK/CK-MB)
  - International Normalized Ratio (INR), if applicable
  - Activated Partial Thromboplastin Time (aPTT)
  - B-type Natriuretic Peptide (BNP) or NT-proBNP
  - Liver Panel:
    - ALT
    - AST
    - Albumin
  - Sodium
  - Potassium
- Neurological Assessments:
  - National Institute of Health Stroke Scale (NIHSS)
  - Modified Rankin Score (mRS)
  - Mini-Mental State Exam (MMSE-2:SV)
  - Additional Neurological testing:
    - Visual Fields Testing
    - Gait Assessment
    - Hand Function
    - Writing Evaluation
    - Drawing Assessment
- 12-lead Electrocardiogram (ECG)
- 6 Minute Walk Test
- Quality of Life Questionnaires
  - Questionnaires may be administered any time after the subject has provided informed consent but should be collected prior to informing the subject of their treatment assignment
- Adverse Event Review

---

### C.4.7 *Transcatheter Aortic Valve Implant or Surgical Aortic Valve Replacement Procedure*

#### C.4.7.1 TAVI

##### **General Procedural Considerations**

Transcatheter Aortic Valve Implantation (TAVI) requires meticulous preparation and typically a multi-disciplinary team approach involving among others, interventional cardiologists, cardiac imaging specialists, cardio-thoracic surgeons and anesthesiologists.

***Within the United States, additional requirements apply for composition of the intra-operative team for TAVI procedures. Requirements are outlined in Appendix R.25.***

In case of significant coronary artery disease that requires revascularization, the Heart Team will assess the feasibility of performing PCI simultaneously with the TAVI procedure based on the coronary lesion characteristics. When it is anticipated PCI can be performed in timely fashion with only a limited amount of additional contrast medium it is encouraged to perform PCI concomitant with the TAVI. When PCI is deemed challenging requiring relatively more time and contrast medium, staged PCI is recommended: TAVI will then be performed at least 7 days after PCI.

The implantation procedure itself takes place either in a catheterization laboratory with adequate hygiene precautions or ideally in a hybrid operating room equipped for state-of-the-art transcatheter and/or surgical procedures.

The execution of the TAVI involves an operating team typically consisting of 1 or 2 operators, an anesthesia team and at least 2 nurses/technicians. Medtronic representative(s) (eg. Therapy Development Specialists, proctors, etc.) may be present during TAVI procedures for training process, to perform valve loading or to provide general case support.

Both the dedicated “valve team” and the operators should have the expertise to select the appropriate access route and device size on a patient-per-patient basis.

All patients undergoing TAVI should be treated using the iliofemoral access route by default (first treatment strategy). Additional non-iliofemoral access routes will only be used in case iliofemoral access is not feasible. Alternative access is limited to subclavian and direct aortic.

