## R.10 Interactive Voice/Web Response System (IXRS)

Medtronic will utilize an Interactive Voice/Web Response (IXRS) System to manage subject screen failures and randomization into the Medtronic CoreValve™ SURTAVI Trial.

The IXRS system will assign patients a Screening ID to be used for all patients that sign the Informed Consent Form and are considered for possible enrollment by the Heart Team. If a patient is screened and does not meet eligibility criteria, the IXRS system will capture the reason for screen failure and disposition of the patient (if known).

Upon meeting eligibility criteria, the IXRS system will randomize the patient and assign a Subject ID to be used in the Oracle Clinical Database upon enrollment.

The IXRS system will assign subjects within one of four groups:

- TAVI with planned PCI
- TAVI without planned PCI
- SAVR with planned CABG
- SAVR without planned CABG

Users can sign in to the Medtronic CoreValve™ SURTAVI Trial study web site by using the URL below and use the sign in box labeled "IVRS/IWRS Login":

[www.bracketglobal.com/client-login](http://www.bracketglobal.com/client-login)

The first time a user accesses the study website, they will be prompted to update their password. The password must be at least 8 characters in length and contain at least 1 capital letter and 1 number or symbol.

Remember that the User ID and Password are private and should not be shared with other individuals.

For technical questions, contact UBC Technical Support at [contact] or at [[contact]](mailto:[contact])

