### Follow-up and Data Collection

Data regarding subject radiation exposure will be collected at all protocol intervals where radiation test or procedures are required.

- Screening
- Index-Procedure (TAVI only)
  - Percutaneous Coronary Intervention (PCI) – if staged approach
- Reintervention (Valve related)

NOTE: Based on the protocol design, imaging required at screening may have been completed prior to the subject signing the informed consent form and data related to radiation exposure during the acquisition of the images may not be available. **Radiation exposure data missing from the subject record will not be considered a protocol deviation.**

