#### C.3.6.2 Exclusion Criteria

Subjects are NOT eligible for trial participation if they meet ANY of the following exclusion criteria:

1. Subject has refused surgical aortic valve replacement (SAVR) as a treatment option;
2. Any condition considered a contraindication for placement of a bioprosthetic valve (i.e. subject requires a mechanical valve);

3. A known hypersensitivity or contraindication to all anticoagulation/antiplatelet regimens (or inability to be anticoagulated for the index procedure), nitinol, or sensitivity to contrast media which cannot be adequately pre-medicated;
4. Blood dyscrasias as defined: leukopenia (WBC <1000mm^3), thrombocytopenia (platelet count <50,000 cells/mm^3), history of bleeding diathesis or coagulopathy;
5. Ongoing sepsis, including active endocarditis;
6. Any condition considered a contraindication to extracorporeal assistance;
7. Any percutaneous coronary or peripheral interventional procedure performed within 30 days prior to randomization (Subjects with recent placement of drug eluting stent(s) should be assessed for ability to safely proceed with SAVR within the protocol timeframe);
8. Symptomatic carotid or vertebral artery disease or successful treatment of carotid stenosis within six weeks of randomization;
9. Cardiogenic shock manifested by low cardiac output, vasopressor dependence, or mechanical hemodynamic support;
10. Recent (within 6 months of randomization) cerebrovascular accident (CVA) or transient ischemic attack (TIA);
11. Active gastrointestinal (GI) bleeding that would preclude anticoagulation;
12. Subject refuses a blood transfusion;
13. Severe dementia (resulting in either inability to provide informed consent for the trial/procedure, prevents independent lifestyle outside of a chronic care facility, or will fundamentally complicate rehabilitation from the procedure or compliance with follow-up visits);
14. Multivessel coronary artery disease with a Syntax score >22 and/or unprotected left main coronary artery (Syntax score calculation is not required for patients with history of previous revascularization if repeat revascularization is not planned);
15. Estimated life expectancy of less than 24 months due to associated non-cardiac co-morbid conditions;
16. Other medical, social, or psychological conditions that in the opinion of the Investigator precludes the subject from appropriate consent or adherence to the protocol required follow-up exams;

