#### C.4.9 Follow-Up Evaluations

All randomized subjects will undergo in-clinic follow-up evaluations at the following time points post implant.

All follow-up periods are defined as the number of days after the date of the index procedure (TAVI or SAVR).

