##### Day 0 = day of index procedure (TAVI or SAVR):

- 30 days (- 7 days and + 14 days)
- 3 months (90 ± 14 days)
- 6 months (180 ± 30 days)
- 12 months (365 ± 30 days)
- 18 months (545 ± 60 days)
- 24 months (730 ± 60 days)
- 3 years (1080 ± 60 days)
- 4 years (1440 ± 60 days)
- 5 years (1800 ± 60 days)

All randomized subjects will complete long-term follow-up through at least 5 years. Based on clinical assessments or regulatory requirements, follow-up may be extended to up to 10 years post-index procedure. Upon completion of the final protocol visit (discontinuation) subject participation will be considered complete and the patient should then be followed per the local standard of care for their condition.

Note: For subjects where the Index Procedure is never attempted (eg. subject withdraws consent for the procedure but agrees to complete follow-up) follow-up intervals will be calculated from the 31st days post-randomization (i.e. the 1st day after the 30 day window from randomization to complete the Index Procedure).

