## C.6 Statistical Methods and Analysis

### C.6.1 Statistical Considerations and Analysis

This section describes the statistical considerations and analysis plans for the SURTAVI trial. The statistical analysis will be performed by the statistics department of Medtronic. As primary analysis all randomized subjects will be analyzed following the modified intention to treat (mITT) approach; ie. analyses will be conducted on the cohort of subjects who undergo an attempted trial treatment, analyzed according to the randomized assignment. A secondary analysis of key objectives will be performed according to the therapy actually received.

Roll-in subjects will not be included in the primary or secondary analysis; however, the data will be summarized separately with descriptive statistics.

All follow-up periods are defined as the number of days after the procedure date.

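### The Table 3 footnote bars the staged PCI that C.4.7.1 recommends, and in the text available no endpoint window covers events between that PCI and TAVI

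*Combined protocol and SAP*

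**What the plan says.** Planned revascularization is part of the randomized strategy. Appendix R.10 lists "TAVI with planned PCI" as one of four assignment groups. C.3.9 and C.4.7.1 encourage PCI in the same session as TAVI and leave staging to the operator. For PCI expected to need more time and contrast, "staged PCI is recommended: TAVI will then be performed at least 7 days after PCI".

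Three timing rules bear on that PCI:

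- C.4.5: "Subjects must have their TAVI or SAVR procedure no later than 30 days post-randomization".
- Exclusion 7 in C.3.6.2 bars "Any percutaneous coronary or peripheral interventional procedure performed within 30 days prior to randomization".
- The asterisk footnote to Table 3 asks sites to recheck, at the procedure, exclusions tied to the index procedure. It gives percutaneous coronary or peripheral intervention and acute MI as examples of what must not have happened in the preceding 30 days. It makes no exception for a planned PCI.

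For the endpoints, C.4.9 sets Day 0 at TAVI or SAVR, and C.6.1 adds "All follow-up periods are defined as the number of days after the procedure date". In O.2, all-cause mortality counts deaths following a valve intervention. Both MI categories (before and after 72 hours) run from the index procedure. AKI is a creatinine change up to 7 days after the index procedure, relative to Baseline, and C.4.6 draws Baseline laboratory tests within 14 days before that procedure. In the SAVR arm, C.3.9 and C.4.7.2 place CABG in the same operation as the valve.

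**The concern.** There are two separate problems.

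First, sites receive instructions that cannot all be followed. A site that stages the PCI as C.4.7.1 recommends, and keeps the 30-day deadline, fails the footnote's check on the day of TAVI. It must then log a deviation or hold back the assigned treatment.

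Second, the two arms' revascularization is not counted alike. Complications of CABG fall inside every window because CABG is part of the index operation. Read literally, a death, MI or AKI after the staged PCI and before TAVI falls outside the mortality, MI and AKI definitions. The creatinine reference can also already reflect contrast injury from the PCI, and C.4.7.1 recommends staging precisely when more contrast is expected. The gap can lower counts only in the TAVI arm. The exposed endpoints are AKI, which enters MAE and (at Stage 2 or 3) Early Safety, and early MACCE.

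**Working it through.** **Inputs.** Gap of at least 7 days from PCI to TAVI (C.4.7.1); TAVI by day 30 after randomization (C.4.5); PCI after randomization (R.10 with exclusion 7); 30-day bar before the index procedure (Table 3 footnote); Baseline within 14 days before the index procedure (C.4.6). The plan states no figure of its own on this point.

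**Permissible schedules.** Let the PCI be on day p after randomization and TAVI on day t, with p ≥ 0, t ≤ 30 and t − p ≥ 7. Then p runs from 0 to 23, and each p allows 24 − p values of t.

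- Total: 24 + 23 + … + 1 = 24 × 25 / 2 = 300.
- A gap g = t − p runs from 7 to 30 days and occurs 31 − g times.

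**Footnote.** Every gap is 30 days or less, so 300 of 300 schedules breach it. If a gap of exactly 30 days is allowed, one schedule is spared and 299 breach. This follows directly from the deadline: a PCI on or after day 0 cannot precede a TAVI due by day 30 by more than 30 days. Exclusion 7 is anchored to randomization, so none of the 300 schedules breaches it.

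**AKI baseline.** For g ≥ 15, the whole 14-day Baseline window lies after the PCI. That happens in 16 + 15 + … + 1 = 16 × 17 / 2 = 136 schedules (136/300 = 45%). In the other 164, Baseline may be drawn before or after the PCI. These are counts of schedules, not patient frequencies.

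An illustration with invented values: creatinine is 1.0 mg/dL before PCI, 1.4 after PCI and 2.1 after TAVI. Against a post-PCI Baseline the rise is 2.1/1.4 = 150%, Stage 1. Against the pre-PCI value it is 2.1/1.0 = 210%, Stage 2, which counts in Early Safety.

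**Windows side by side.**

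| Item | CABG with SAVR | Staged PCI, before TAVI |
|---|---|---|
| Day 0 (C.4.9, C.6.1) | same day | 7–30 days earlier |
| Death (O.2) | covered | precedes the valve intervention |
| MI (O.2) | covered | fits neither category |
| AKI (O.2) | covered | before the 7-day window |
| Bleeding, stroke, vascular (O.2) | covered | definitions not index-anchored; ambiguous under the general Day-0 rule |

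**Order of magnitude for the primary endpoint.** The documents give neither the frequency of staging nor event rates before TAVI. As assumptions only: planned revascularization 15–25%, staged in 10–60% of those, death or disabling stroke before TAVI 1–3%.

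- Middle: 0.20 × 0.30 × 0.02 = 0.12 percentage points, about 1 of 800 TAVI subjects.
- Range: 0.15 × 0.10 × 0.01 = 0.015 to 0.25 × 0.60 × 0.03 = 0.45 percentage points.
- The margin is 7 points, so the middle value is 0.12/7 = 1.7% of it. The standard error of the difference at 17% with 800 per arm is √(2 × 0.17 × 0.83 / 800) = 1.88 points.

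This product is gross. It subtracts no background waiting-time risk, and it counts disabling stroke as lost although that definition is not index-anchored. It therefore overstates the one-sided part.

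**The case against.** The strongest reply is that the absence of a rule can be claimed only for the text available. C.6.5.2 sends further analysis detail to the SAP, and C.5.3 leaves event-classification rules to the CEC charter; neither is shown. That stands, and no sentence shown discards events before Day 0. A reader might infer that such events will be dropped, but the documents do not say so.

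Next, C.5.2 collects adverse events from enrollment, and C.6.4.2 and C.6.7.2 plan ITT analyses. These record the events and retain the subjects, but do not assign the events to a window. For subjects whose index procedure is never attempted, the Note in C.4.9 starts follow-up on day 31 after randomization and does not say how earlier deaths count.

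Appendix R.23 lists "Percutaneous Coronary Intervention (PCI) – if staged approach" under the index procedure, which might seem to settle the matter. The list concerns radiation data. Carried over to the endpoints, with Day 0 at the PCI, a 30-day window would leave only 0 to 23 days after TAVI, and the 7-day AKI window would end no later than the day of TAVI. It would also sit badly with the day-31 Note.

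The footnote can be called an illustrative paraphrase of exclusions 7 and 18, or read as barring only MI. The operative exclusion is indeed compatible, which lowers the severity. The plain reading still covers both items.

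Finally, the MI and AKI windows are VARC-2 definitions, and deaths while awaiting SAVR also precede Day 0. Both points stand. They argue against adding second windows in the TAVI arm alone.

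**Conclusion.** The footnote contradiction holds on the text and needs no assumption about rates. The window gap holds for the visible text only. Its effect on the primary endpoint is probably very small; the figures above illustrate scale under assumed inputs and are not estimates. Early MACCE and AKI are more exposed, by an amount the documents do not let one compute. Severity is minor.

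Two stronger readings are not supported. One is that an MI after the staged PCI removes the subject from mITT. C.6.4.2 defines mITT by an attempted procedure, so a TAVI delayed beyond exclusion 18 and the deadline would be a deviation in a subject who stays in mITT. Only a subject who never reaches TAVI is affected, and the attempt definition might even be read to include the PCI. The other is that the non-inferiority result or a labeling claim is at risk. Nothing in the documents shows a shift of that size.

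**What to change.** 1. Exempt protocol-planned staged PCI from the Table 3 footnote, or anchor its PCI clause to randomization as in exclusion 7.
2. For subjects with a planned staged PCI, use the last pre-PCI creatinine as the AKI reference (for example the screening value in C.4.1). Report deaths, MI and AKI between PCI and TAVI alongside the endpoint results.
3. Add a sensitivity analysis of the primary endpoint, MACCE and MAE on the ITT population, counting all events from randomization in both arms. Include deaths before day 31 in subjects never treated. This treats waiting-time risk alike in both arms and leaves Day 0 and the VARC-2 windows unchanged.

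The cost is protocol and SAP wording, one extra analysis and a little more adjudication. Screening creatinine and adverse events from enrollment are already collected. TAVI event rates may look slightly less favourable.
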